## 8.4 Data sources

South Korea has a universal health coverage system that the National Health Insurance covers approximately 97% of the overall South Korean population. The claims data of Health Insurance Review & Assessment Service (HIRA) contains 46 million patients per year that account for 90% of the total population in Korea and include claims from almost 80,000 healthcare service providers across South Korea as of 2011.

The claims data of HIRA includes patients' diagnosis, treatment, procedures, surgical history, and prescription drugs which provide a valuable resource for healthcare service research. Data elements captured in the HIRA database include patient-level demographic and plan enrollment information (e.g., start and stop dates of health plan enrollment), date-stamped (month and year) inpatient and outpatient medical claims (e.g., diagnosis codes, procedure codes, provider specialty), and pharmacy claims (e.g., prescription fill/refill dates, drug name/code, dosage). While procedure codes that identify patient receipt of laboratory tests are available, actual laboratory values and test results are not available.

The HIRA database has unique attributes that make it a useful data source for this study. The key advantage of the HIRA database relative to other potential data sources (e.g., medical chart review) is that it is a population level data including most of Korean population and it will provide a large analytic sample and provide accurate claim-level treatments pattern and health care utilization across all provider settings (e.g., inpatient, outpatient, pharmacy) in patients' spectrum of care.

One key limitation of the HIRA database is that it does not include clinical variables such as laboratory values and clinical markers. To overcome this limitation, the Charlson comorbidity index and overall healthcare utilization observed during the pre-index period will be used as proxy measures to incorporate the overall health status of the individual patients.

## 8.5 Study size

Based on the 2015-2016 HIRA disease statistics, there are 148,130 – 169,259 patients with atrial fibrillation (KCD code: I48). Thus, we anticipate getting the number of patients with approximately 150,000 since we plan to include patients who already had atrial fibrillation and were prescribed aspirin, warfarin, or NOACs from July 1, 2015 to November 30, 2016. However, the study size might change after applying inclusion and exclusion criteria.

## 8.6 Data management

### Obtaining data files

Pusan National University team will submit the data request form to HIRA. After the HIRA committee review, the data will be uploaded in the server. The study team will access the data through the remote access using IP address. All medical or pharmacy claims and demographic information from January 1, 2007 to November 30, 2016 of patients with atrial fibrillation (KCD code: I48) from July 1, 2015 to November 30, 2016 will be accessed.

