**Figure 1. Study design scheme**

## 8.2 Setting

### 8.2.1 Inclusion criteria

Patients must meet all of the following inclusion criteria to be eligible for inclusion in the study:

1. Patients aged 18 years or older on the index date
2. Patients had  $\geq 1$  medical claim for AF (refer to Table 1) before or on the index date with at least one hospitalization or at least two outpatient visits:

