**Table 1. Diagnosis codes for inclusion criteria.**

KCD-6 	KCD-7 
I48 (Atrial fibrillation and flutter)	I48 (Atrial fibrillation and flutter)
I480 (Atrial fibrillation)	I480 (Paroxysmal atrial fibrillation)
I481 (Atrial flutter)	I481 (Persistent atrial fibrillation)
	I482 (Chronic atrial fibrillation)
	I483 (Typical atrial flutter)
	I484 (Atypical atrial flutter)
	I489 (Atrial fibrillation and atrial flutter, unspecified)

KCD-6, Korean version of ICD-10 (6th revision); KCD-7, Korean version of ICD-10 (7th revision)

1) KCD-6 diagnosis codes will be used from 1 July 2015 to 31 December 2015.

2) KCD-7 diagnosis codes will be used from 1 January 2016 to 30 November 2016.

[NOTE] KCD code is based on ICD-10 and almost similar, but KCD code is slightly different from ICD-10 (e.g., ICD-10 is more subdivided and extensive than KCD code).

3. Patients prescribed aspirin, warfarin, or NOACs during intake period (from July 1, 2015 to November 30, 2016)

*[Note] NOACs include apixaban, dabigatran, and rivaroxaban.*

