### 8.2.2 Exclusion criteria

Patients meeting any of the following criteria will not be included in the study.

1. Medical claims indicating diagnosis or procedure for hip/knee replacement surgery within 6 weeks prior to index date
2. Medical claims indicating a diagnosis code indicative of rheumatic mitral valvular heart disease, mitral valve stenosis during the 12-month baseline period  
(Valvular AF / Prosthetic heart valves)
3. Medical claims indicating a diagnosis code of VTE (Venous thromboembolism) during the 12-month baseline period
4. Medical claims indicating a diagnosis or procedure code of transient AF, or cardiac surgery during the 12-month baseline period

(Thyrotoxicosis, Hypertrophic cardiomyopathy, Elective defibrillation, radiofrequency ablation, or left atrial appendage occlusion)

5. Medical claims indicating a diagnosis code of other conditions during the 12-month baseline period  
(End-stage chronic kidney disease / Kidney transplant / Dialysis / Pericarditis)
6. For the comparison of “NOAC versus NOAC”, and “NOAC versus warfarin”, patients with any OACs (apixaban, dabigatran, rivaroxaban, or warfarin) in the pre-index period (from 1 year prior to the day before index date)
  - *[NOTE] Patients prescribed antiplatelets in the pre-index period will not be excluded.*
7. For the comparison of “NOAC versus aspirin”, patients with following medications in the pre-index period (from 1 year prior to the day before index date)
  - NOAC user: OACs (apixaban, dabigatran, rivaroxaban, warfarin)
  - Aspirin user: none
  - *[NOTE] NOAC user is defined as OAC naïve user and aspirin user is allowed to have OACs or antiplatelets in the pre-index period.*

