 - A. Sub-dataset 7: patients with index treatment of apixaban and patients with index treatment of aspirin
 - B. Sub-dataset 8: patients with index treatment of dabigatran and patients with index treatment of aspirin
 - C. Sub-dataset 9: patients with index treatment of rivaroxaban and patients with index treatment of aspirin

[NOTE] The index date will be defined as date of the first prescription of NOAC or aspirin in patients with NVAF during the intake period (from July 1, 2015 to November 30, 2016). To identify NOAC users, a look-back observation period from 1 year prior to the day before the index date will be used and must indicate no OAC use during this period. However, OAC use or antiplatelet use during a look-back observation period from 1 year prior to the day before the index date will be allowed for aspirin users. The diagnosis date of NVAF could occur from January 1, 2007 up to and including the index date.

Each patient was followed until discontinuation or switching of index treatment, outcome occurrence, or study ends (November 30, 2016).

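### The data request admits only patients with an I48 claim between July 2015 and November 2016, which may fall after the index date, so entry to the NOAC-versus-aspirin cohorts can depend on post-index events

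*Protocol*

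**What the plan says.** **The extract.** Protocol 8.6 (Obtaining data files) asks for "All medical or pharmacy claims and demographic information from January 1, 2007 to November 30, 2016", but only "of patients with atrial fibrillation (KCD code: I48) from July 1, 2015 to November 30, 2016 will be accessed". The I48 condition is not tied to the index date. It closes on 30 November 2016, the day follow-up ends.

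**Eligibility.** Inclusion criterion 2 (Protocol 8.2.1, repeated in SAP 3.1) needs AF "before or on the index date with at least one hospitalization or at least two outpatient visits". SAP 3.1 dates this explicitly for every comparison: "The diagnosis date of NVAF could occur from January 1, 2007 up to and including the index date". The Protocol abstract and SAP 2.1 also look back to 2007.

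**AF codes.** The footnotes to Table 1 cover only the intake window. The earlier code set is dated as follows: "KCD-6 diagnosis codes will be used from 1 July 2015 to 31 December 2015". No code set is given for 2007 to June 2015.

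**Index date and washout.** For NOAC versus aspirin the index is the "date of the first prescription of NOAC or aspirin in patients with NVAF during the intake period". No AF code is required on that prescription. NOAC users must be free of oral anticoagulants in the preceding year, but an "aspirin user is allowed to have OACs or antiplatelets in the pre-index period".

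**The concern.** The filter that decides who is in the files is narrower than the eligibility rule, and it can be satisfied after time zero. Take a patient whose AF claims all predate July 2015 and whose index visit carries no I48 code. That patient meets every inclusion criterion but reaches the analyst only if I48 is recorded later, possibly at the outcome admission itself. Inclusion is then conditional on the future.

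This matters if later coding is related to outcome and the affected share differs by arm. Outcomes are hospital claims with all diagnosis positions searched, so an admission is one more occasion to record I48. Patients starting an oral anticoagulant are likely to be coded with AF around that visit. Long-term aspirin users may not be. Because aspirin has no washout, their first in-window fill will often come early in the window, leaving little in-window time before index.

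Matching, weighting and covariate adjustment (SAP 5.1) balance baseline variables among patients already in the files, so they cannot undo this selection. The only sensitivity analysis planned is multinomial IPTW. Protocol 8.9.3 (Selection Bias) does not mention the issue.

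**Working it through.** **No plan figure to reproduce.** Neither document quantifies coding frequency or selection. The anticipated study size of about 150,000 is not a power calculation. It lies close to the 2015 I48 count (150,000/148,130 = 1.013), and the point does not rest on it.

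**1. Who is affected.** Every eligible patient falls into one of three groups:
- I48 coded between 1 July 2015 and index: in the files whatever happens later.
- No such claim, but I48 coded after index and by 30 November 2016: in the files because of a post-index record.
- No such claim and none later: eligible under SAP 3.1 but absent from the files.

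**2. Simple formula.** All inputs are assumptions.
- f = share of eligible aspirin users with no in-window I48 by index
- p = chance of a later I48 claim for those of them without an event
- s = the same chance for those with an event

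The share included is (1−f)+f·s with an event and (1−f)+f·p without. Events are taken as rare, so the aspirin rate is multiplied by about [(1−f)+f·s]/[(1−f)+f·p]. With f = 0 for NOAC, a true HR of 1.00 appears as the inverse of that factor.

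| f | p | s | Factor | Apparent HR |
|---|---|---|---|---|
| 0.1 | 0.9 | 1.0 | 1/0.99 = 1.01 | 0.99 |
| 0.3 | 0.7 | 1.0 | 1/0.91 = 1.10 | 0.91 |
| 0.3 | 0.5 | 1.0 | 1/0.85 = 1.18 | 0.85 |
| 0.3 | 0.9 | 0.7 | 0.91/0.97 = 0.94 | 1.07 |

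The last row represents event patients who die, or otherwise leave care, before I48 is coded again. The direction reverses.

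**3. Relaxing s = 1 and f = 0 for NOAC.** Let r be the chance of a routine post-index I48 claim and c the chance that an event admission carries I48. Then p = r and s = 1−(1−r)(1−c). For example, with aspirin f = 0.4, r = 0.8 and c = 0.9, s = 1−0.2×0.1 = 0.98. The factor is (0.6+0.4×0.98)/(0.6+0.4×0.8) = 0.992/0.92 = 1.078, so the apparent HR is 0.93. Over aspirin f = 0.2–0.6, NOAC f = 0–0.05, r = 0.5–0.95 and c = 0.5–0.9, the apparent HR runs from 0.72 to 1.00. The 0.72 needs f = 0.6 with r = 0.5: 0.97/0.70 = 1.386. This form forces s ≥ p, so it cannot show the reversal in step 2.

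**4. Sensitivity to routine coding.** A simulation with a true rate ratio of 1 used 3 million patients per arm, the 519-day window, 3 events per 100 person-years, c = 0.9, NOAC f = 0.03 and aspirin f = 0.2–0.6. It gave these NOAC-versus-aspirin ratios:
- 0.5 routine I48 claims a year: 0.68–0.91
- 1 a year: 0.83–0.95
- 2 a year: 0.94–0.98
- 4 a year: about 1.0

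Before the I48 selection was applied, the ratio was 0.99–1.01, which is simulation noise.

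**5. Sub-datasets 1–6.** At f = 0.05 the factor is 1.00–1.02 in each arm (same r and c ranges as step 3). If coding is similar in both arms, most of even that cancels.

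**The case against.** **The documents may already require an in-window code.** The Table 1 footnotes date the AF codes to the intake window. Read with criterion 2, this could mean I48 inside the window and on or before index, in which case no one would enter through a later claim. Protocol 8.6 is also a short summary, and the request form itself is not available. This does not displace the explicit January 2007 look-back, which SAP 3.1 states for all three comparisons. What stands is that a third place must be reconciled.

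**The direction is not established.** A reader might infer that patients with events are over-included and that the study is therefore biased towards NOACs. The documents do not support that as fact. They give no coding rates, Protocol 8.9.3 says mortality data are incomplete, and the last row of the table shows that modest under-coding after an event reverses the sign.

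**The larger distortions need infrequent coding.** Continuing aspirin users tend to index early and so have up to about 16–17 months to collect a routine I48 claim. The group with the highest f therefore tends to have a high p as well. This stands and pulls the likely size towards 1.

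**It is not study-wide.** A reader might also extend the concern to every comparison. Anticoagulant starters are probably coded at or near index in both arms of sub-datasets 1–6. All comparative analyses are also contingent on feasibility.

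**Conclusion.** The mismatch is real: under Protocol 8.6 as written, some patients who satisfy SAP 3.1 are in the files only because of a claim made after index. The consequence is a possible bias, mainly in sub-datasets 7–9. If event admissions add I48 codes, it would favour NOACs. A null HR would then appear as about 0.85–0.99 for f = 0.1–0.3 and p = 0.5–0.9, taking every event patient as included and f = 0 for NOAC. More extreme assumptions widen this to 0.72, or 0.68 in the simulation. Frequent routine coding (about four I48 claims a year) brings it to about 1.0, and deaths after an event without later coding could take it above 1. All these inputs are assumed. The direct evidence would be the per-arm count of patients whose first in-window I48 claim follows index, and the plan does not ask for it.

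**What to change.** Reconcile Protocol 8.6, the Table 1 footnotes and SAP 3.1 on when the AF claim must occur, and state which AF codes apply before July 2015 if the 2007 look-back is kept. Then do one of the following:

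1. **Widen the request** to all patients with a study-drug prescription in the intake period and any I48 claim from 2007 onward, and apply the on-or-before-index rule afterwards. Every eligible patient is then in the files whatever happens later, so the inclusion factor is 1.00. The cost is a revised data application. Protocol section 5 planned data collection from 1 February 2018, so this may come late.
2. **Keep the extract** and restrict both arms to patients with an I48 claim from 1 July 2015 to the index date inclusive, at least as a sensitivity analysis for sub-datasets 7–9. Everyone in that set is in the files regardless of outcome. It needs one more eligibility line and no new data. The cost is lost patients, mainly aspirin users who index early in the window, and some precision.

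Under option 2, leave the index date as the first study-drug prescription in the window. Moving it to the first fill on or after the I48 claim would be asymmetric. Exclusion criterion 7 would then remove NOAC starters whose first fill preceded the claim, while aspirin users in the same position would simply be re-indexed.

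In either case, report per arm how many patients have their first in-window I48 claim only after index. If the extract is not widened, add the issue to Protocol 8.9.3.

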## 8.7 Data analysis

- All outcome variables will be summarized descriptively through the tabular and graphical display of mean values, medians, ranges, and standard deviations of continuous variables of interest and frequency distributions for categorical variables.
- Patients with aspirin, warfarin, and NOACs will be matched via propensity-score method. Patients will be matched on patient demographics (i.e., age, sex) and clinical (i.e., CHA2DS2-VAsC score, Charlson Comorbidity Index score, etc) variables. Other propensity score method (i.e., covariate adjustment, inverse probability of treatment weighting (IPTW)) will also be used. A Cox proportional hazards model, to account for differences in follow-up time and right data censoring, will be used to compare effectiveness and safety outcomes between treatment groups.
- Comparative analyses will be performed contingent on a feasibility assessment based on the descriptive analyses
- All analyses will be carried out using SAS version 9.4. The 95% confidence intervals for the estimates will be calculated and p < 0.05 considered significant.
- Sensitivity analysis of performing IPTW using the propensity score derived from multinomial model will be conducted.

Detailed methodology for summary and statistical analyses of data collected in this study will be documented in a Statistical Analysis Plan (SAP), which will be dated, filed and maintained by the sponsor. The SAP may modify the plans outlined in the protocol; any major modifications of primary endpoint definitions or their analyses would be reflected in a protocol amendment.

## 8.8 Quality control

The HIRA data files are large and complex. The study analysts will thoroughly evaluate and assess the data quality—including review of data for accuracy, consistency, and completeness—by generating descriptive summaries of variables to be used for study analysis. To ensure the integrity and quality of data and study results, the study team will implement several practice standards for statistical programming, database management, and documentation for all projects involving database analyses. The following three steps will be undertaken to achieve this high level of quality:

- Documentation of SAS programming
  - To ensure smooth transition of analytic methods and work among programmers, reviewers, and other project personnel, documentation of the following information will be created for each SAS program: Project name; Program name; Program purpose; Program author; Date the program was completed;

Descriptions of subsequent changes and/or enhancements, with name of programmer and date for each.

- Validation of SAS programs
  - We will conduct following programming validation methods: Log review; Review of data listings and tables of summary statistics.
- Database storage and retention
  - The HIRA data is not allowed to be possessed by individual researcher. The data will be stored in the server owned by HIRA and will be only accessed through the remote access. Thus, the study team will not be able to store and possess the data. Two researchers will be allowed to access the data at once since only two IP addresses will be provided by HIRA. To ensure the integrity of the original data files, the data will be stored on a Linux server in a designated folder that cannot be overwritten. Data sets derived from the original files during the analysis process will be stored in a separate folder.

## **8.9 Limitations of the research methods**

### **8.9.1 Measurement Error(s)/Misclassification(s)**

In general, all study measures will be defined by information available in the claims data in the form of diagnosis codes, procedure codes, drug codes, and dates of service. Patients were identified for study inclusion on the prescription claims, which (as with all claims-based studies) are subject to coding error. Patient charts were not available to validate the accuracy of case identification.

### **8.9.2 Information Bias**

Information bias is less likely to occur since the HIRA data is a population level data which covers the whole population in Korea which has a universal health insurance system.

### **8.9.3 Selection Bias**

This study will include only those patients who filled a prescription through their insurance for aspirin, warfarin, or NOACs. Patients who did not fill a prescription through their insurer (i.e., patients who received free samples or paid for the medication out of pocket) cannot be evaluated in an administrative claims database.

Since the HIRA database does not include eligibility data and the complete mortality data for beneficiaries, the continuous health plan enrollment cannot be ensured and the deceased could be included in the analysis.

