Exclusion criteria	Exclusion criteria	HIRA database	
Claims with the following KCD codes or procedure codes:
 
 
1. Valvular AF/ Prosthetic heart valves: I05, I08, I09, I34, Q23, T820, T826, Z952, Z953, Z954            - Korean procedure codes: M6580, M6581, M6582, O1791, O1792, O1793, O1794, O1795, O1796, O1797, O1798, O1799, M6531, M6532, M6533, O1690, O1730, 1740, O1750, O1760, O1770, O1781, O1782, O1783, O1810, O1826
 
2. End-stage of chronic kidney disease/dialysis: N185, T824, Y602, Y612, Y622, Y841, Z49, Z992, E1022, E1122, E1222, E1322, E1422
 
3. Kidney transplant: Z940
 
4. Venous thromboembolism: I636, I676, I801, I802, I803, I808, I809, I81, I822, I823, I829, I26
 
5. Hip or knee replacement            - Korean procedure codes: N0711, N0715, N1711, N1715, N1721, N1725, N2070, N2072, N2077, N2710, N2712, N2717, N3710, N3712, N3717, N3720, N3722, N3727, N4710, N4712, N4717, N4720, N4722, N4727
 
6. Thyrotoxicosis: E05
 
7. Pericarditis: I30, I31, I32
 
8. Hypertrophic cardiomyopathy: I422
 
9. Elective defibrillation, radiofrequency ablation, or left atrial appendage occlusion            - Korean procedure codes: M5880, M6540, M6542, M6545, M6547, M6511
 

Follow-up period	Follow-up period	HIRA database	
From the index date until the first occurrence of the following whichever came first:
 
 
1. Discontinuation: maximum of a 30-day gap after the calculated time to finishing the pack based on pack size and number of tablets per day. Switching: switch to any other study drugs
 
2. Outcome occurrence
 
3. Study ends: November 30, 2016
 

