3 ANALYSIS SETS/ POPULATIONS

3.1 FULL ANALYSIS SET

Inclusion criteria

Patients must meet all of the following inclusion criteria to be eligible for inclusion in the study:

1. Patients aged 18 years or older on the index date
2. Patients had ≥ 1 medical claim for AF (refer to Table 1) before or on the index date with at least one hospitalization or at least two outpatient visits:

[Diagnosis codes for inclusion criteria]

KCD-6 ¹⁾	KCD-7 ²⁾
I48 (Atrial fibrillation and flutter)	I48 (Atrial fibrillation and flutter)
I480 (Atrial fibrillation)	I480 (Paroxysmal atrial fibrillation)
I481 (Atrial flutter)	I481 (Persistent atrial fibrillation)
	I482 (Chronic atrial fibrillation)
	I483 (Typical atrial flutter)
	I484 (Atypical atrial flutter)
	I489 (Atrial fibrillation and atrial flutter, unspecified)

KCD-6, Korean version of ICD-10 (6th revision); KCD-7, Korean version of ICD-10 (7th revision)

1) KCD-6 diagnosis codes will be used from 1 July 2015 to 31 December 2015.

2) KCD-7 diagnosis codes will be used from 1 January 2016 to 30 November 2016.

[NOTE] KCD code is based on ICD-10 and almost similar, but KCD code is slightly different from ICD-10 (e.g., ICD-10 is more subdivided and extensive than KCD code).

3. Patients prescribed aspirin, warfarin, or NOACs in intake period (from July 1, 2015 to November 30, 2016)
[Note] NOACs include apixaban, dabigatran and rivaroxaban.

Exclusion criteria

Patients meeting any of the following criteria will not be included in the study.

1. Medical claims indicating diagnosis or procedure for hip/knee replacement surgery within 6 weeks prior to index date
2. Medical claims indicating a diagnosis code indicative of rheumatic mitral valvular heart disease, mitral valve stenosis during the 12-month baseline period
(Valvular AF / Prosthetic heart valves)
3. Medical claims indicating a diagnosis code of VTE (Venous thromboembolism) during the 12-month baseline period
4. Medical claims indicating a diagnosis or procedure code of transient AF, or cardiac surgery during the 12-month baseline period
(Thyrotoxicosis, Hypertrophic cardiomyopathy, elective defibrillation, radiofrequency ablation, or left atrial appendage occlusion)
5. Medical claims indicating a diagnosis code of others during the 12-month baseline period
 - (End-stage chronic kidney disease / Kidney transplant / Dialysis / Pericarditis)

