4.3 OTHER ENDPOINTS

Table 3. Other Endpoints

Variable	Role	Operational definition
Discontinuation	Outcome	Discontinuation is defined as the first day of a period of at least 30 consecutive days after the calculated time to finishing the pack based on pack size and number of tablets per day. The date of discontinuation will be the end date of the last filled prescription before the treatment gap.
Switching	Outcome	A switch among anticoagulants will be defined as a prescription filled for non-index OAC within 30

Variable	Role	Operational definition
		days after the date of discontinuation.
Clinical events preceding each pattern	Outcome	
Types of event* preceding each pattern (i.e., discontinuation, switching)
 
[*Note] Events will include but not limited to (1) serious clinical events where physicians might consider changing anticoagulants (e.g., thromboembolic events (e.g., stroke/systemic embolism, venous thromboembolism [codes in Table 7]), major bleeding [codes in Table 8]); (2) the occurrence of a contraindication for OACs (e.g., valvular atrial fibrillation, severe kidney disease); and (3) procedure for atrial fibrillation that might not require OACs (e.g., elective defibrillation, radiofrequency ablation, and left atrial appendage occlusion [codes in Table 13]).

Compliance (medication possession ratio, MPR)	Outcome	
Medication possession ratio (MPR) will be calculated as total days of index treatment dispensed / 365 days of study follow-up.
 
Patients with an MPR greater than 1 will be capped at 1.

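### Death and disenrolment are in neither follow-up list, so a death that leaves a 30-day supply gap is recorded as discontinuation, and the documents disagree on whether enrolment dates are held

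*Protocol*

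**What the plan says.** **What the data hold.** Protocol 8.4 lists "start and stop dates of health plan enrollment" among the captured elements, and SAP 2.1 repeats this. Protocol 8.9.3 gives the opposite premise, "Since the HIRA database does not include eligibility data and the complete mortality data for beneficiaries", and concludes that continuous enrolment cannot be ensured and that deceased patients could be in the analysis.

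**When follow-up ends.** Protocol 8.3 runs follow-up "From the index date until the first occurrence of the following whichever came first": discontinuation or switching, outcome occurrence, and "Study ends: November 30, 2016". SAP 3.1 gives the same reasons. Death and disenrolment appear in neither list.

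**What counts as discontinuation.** SAP 4.3, Table 3, defines it as a gap of at least 30 consecutive days after the supply should have run out. On dating, it says: "The date of discontinuation will be the end date of the last filled prescription before the treatment gap". The definition does not ask whether the patient is alive or still in care, and Protocol 8.9.5 says the database does not record why treatment stopped.

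**How it is analysed.** Drug utilization falls under primary objective 1 and secondary objective 1. SAP 6 assigns it chi-square and t-tests; propensity-score methods and Cox models are assigned only to stroke/systemic embolism and major bleeding. The only named sensitivity analysis (Protocol 8.7, SAP 5.1) is IPTW from a multinomial propensity model.

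**The concern.** A programmer cannot tell from the documents whether enrolment dates can be used to end follow-up. Under the rules as written, a death is absorbed into the discontinuation endpoint.

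The drugs being compared may be given to patients of different age and comorbidity, and so with different mortality. A drug used in sicker patients would then appear to have poorer persistence even if living patients stayed on it equally well. The SAP 6 row for utilization does name demographic and clinical characteristics as covariates, but chi-square and t-tests do not adjust for them.

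Two neighbouring endpoints in Table 3 share the problem. The medication possession ratio divides by a fixed 365 days, so an early death reads as poor compliance. The tabulation of clinical events before discontinuation would show a fatal stroke or bleed as an event followed by stopping the drug.

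**Working it through.** The documents state no mortality, discontinuation rate or days' supply, so there is no figure to reproduce. Every rate below is an assumption.

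**1. Trace one death through the rules.** The patient dies with tablets in hand and fills nothing more. Supply runs out, 30 days pass, and Table 3 records discontinuation dated to the end of the last fill. If the gap cannot complete before 30 November 2016, the patient is instead censored at study end. No step separates this patient from a living one who stopped.

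**2. Share of recorded discontinuations that are deaths.** Take constant, independent hazards, with m annual mortality and d true 12-month discontinuation:

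- h_m = -ln(1 - m), h_d = -ln(1 - d), share = h_m / (h_m + h_d).
- m = 3%, d = 60%: 0.0305 / (0.0305 + 0.9163) = 3.2%.
- m = 5%, d = 40%: 0.0513 / (0.0513 + 0.5108) = 9.1%.
- m = 10%, d = 30%: 0.1054 / (0.1054 + 0.3567) = 22.8%.

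With wider assumptions (discontinuation at 0.2 to 0.8 per year, death at 0.03 to 0.10 per year), the share runs from 0.03/0.83 = 3.6% to 0.10/0.30 = 33.3%.

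**3. Distortion of a comparison between drugs.** Let true discontinuation be 40% for both. Recorded 12-month discontinuation = 1 - (1 - d)(1 - m):

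| Annual mortality | Recorded discontinuation |
|---|---|
| 3% | 1 - 0.60 × 0.97 = 41.8% |
| 5% | 1 - 0.60 × 0.95 = 43.0% |
| 10% | 1 - 0.60 × 0.90 = 46.0% |

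A contrast of 5% v 3% mortality produces a spurious difference of 1.2 percentage points; 10% v 3% produces 4.2 points. The second pairs opposite ends of the assumed range and is an extreme illustration. The formula also dates each death's discontinuation within the same 12 months, whereas it is really dated at the end of supply.

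**4. Effect on the treated-arm Cox models.** Time counted after death is capped at leftover supply, plus up to 30 days if follow-up runs through the gap. With death rate r, days' supply S and gap time g, and death on average halfway through a fill:

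- Post-death share of person-time = r × (S/2 + g) / 365.
- Lowest: 0.03 × 15 / 365 = 0.12%. Highest: 0.10 × (45 + 30) / 365 = 2.05%.
- Hazard-ratio factor with e = (S/2 + g)/365: (1 + r0·e) / (1 + r1·e).
- 5% v 3%, S = 30, g = 0: 1.0008. At 15% v 5%, S = 90, g = 30: 1.0203.

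The factor is about 1.00 to 1.02 even with a threefold mortality difference.

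**The case against.** **It is disclosed.** Protocol 8.9.3 admits that the deceased may be included and 8.9.5 that reasons for stopping are unknown. That stands as disclosure, but it gives no handling rule. Protocol 8.6 gives the team all medical and pharmacy claims to 30 November 2016, which can separate patients still in care from those with no further claims. They cannot separate death from non-use of care.

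**The comparative results are safe.** This largely stands. A reader might infer that dead patients' event-free time materially biases the stroke and bleeding hazard ratios. In treated arms it does not, because follow-up is on-treatment and the excess is capped (step 4). The cap does not cover the untreated group of secondary objective 2, which has no supply end.

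**A hazard ratio for persistence would overstate the case.** The step 3 assumptions at 10% v 3% imply an apparent discontinuation hazard ratio of (0.511 + 0.105) / (0.511 + 0.030) = 1.14. The plan estimates no such ratio, and the inputs are the two ends of an assumed range. At 5% v 3% it is about 1.04.

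**Loss of coverage is probably rare.** This stands. Protocol 8.4 describes a universal system with National Health Insurance covering about 97% of the population. Death is the main issue.

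**Requiring a later claim uses future information.** This is true. With at most 518 days from the start of intake to study end, some living late stoppers will have no later claim. It is a reason to report the group separately and keep an all-gaps sensitivity analysis.

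**Conclusion.** The point holds for the utilization results. The two statements on enrolment data conflict in current text, neither follow-up list contains death or disenrolment, and the discontinuation rule absorbs deaths that leave a completed gap. If the assumed rates are near the truth, deaths are a noticeable minority of recorded discontinuations, about 3-23%. Unequal mortality could then move an unadjusted comparison by roughly 1 to 4 percentage points, the upper end being extreme. These sizes rest on assumed, constant and independent hazards.

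The documents do not support extending this to a material bias in the treated-arm stroke, embolism or bleeding hazard ratios. Nor do they show that no death information exists: 8.9.3 says only that mortality data are not complete, and the plan does not say whether any partial records would be used.

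**What to change.** 1. Reconcile Protocol 8.4 and SAP 2.1 with Protocol 8.9.3, and state which enrolment and death information is actually held.
2. If enrolment stop or death dates are held, add them as an end of follow-up in Protocol 8.3 and SAP 3.1, and state in SAP Table 3 that they are not discontinuation.
3. If they are not held, report supply gaps in two groups: *discontinued, with a later claim of any kind*, and *no further claims (death, loss or no care)*. Treat the second as a separate or competing category, and add a sensitivity analysis that counts all gaps as discontinuation.
4. Do not cut Cox follow-up at the last claim. A living patient who fills 90 days on 1 October 2016 and has no later claim would lose 60 valid event-free days. The loss may differ by drug, since Protocol 6 notes regular blood monitoring for vitamin K antagonists. Protocol 8.4 also describes medical claims as stamped only by month and year.

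The cost is amended wording and one variable derived from claims already requested. The downside is that some living patients who stop near study end fall into the no-further-claims group. Tabulating that group by time from end of supply to 30 November 2016 would show how many could be late stoppers.
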